5.2.3 Total Daily Dose

For Total Daily Dose, analysis will be performed using linear mixed effect models to evaluate the effect of personalized teaching of the optimal insulin injection technique in conjunction with the use of disposable BD Micro-Fine Plus 32G pen needles on the response. In the model, subject will be a random effect, time period (baseline, 3 months or end of study), day in each time period, and lipohypertrophy will be fixed effects. Two-way and three-way interactions between fixed effects will be investigated. Only significant interactions will be included in the model. Models will be used to compute estimated mean, difference between baseline and end of study, and corresponding two-sided 95% CI for responses of interest.

5.2.4 Blood Glucose

For 24 Hour Average Blood Glucose, analysis will be performed using linear mixed effect models to evaluate the effect of personalized teaching of the optimal insulin injection technique in conjunction with the use of disposable BD Micro-Fine Plus 32G pen needles on the response. In the model, subject will be a random effect, time period (baseline, 3 months or end of study), day in each time period and lipohypertrophy will be fixed effects. Two-way and three-way interactions between fixed effects will be investigated. Only significant interactions will be included in the model. Models will be used to compute estimated mean, difference between baseline and end of study, and corresponding two-sided 95% CI for responses of interest.

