2.6 Acceptance Criteria

There is no acceptance criteria for this study.

3 Intended Statistical Software and Data Information

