5.1 Derived Variables

5.1.1 Total Daily Dose

Total Daily Dose will be calculated as the sum of basal and bolus insulin dose per day from both diary data and CRF. The data from the two sources will be analyzed separately.

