5.1.3 Blood Glucose

24 Hour Average Blood Glucose and other glycemic variability variables (such as MAGE, time in range, etc.) will be computed from BGM data using BD proprietary *extractGlucoseVariabilityFeatures()* and *summarizeGlycemicVariability()* functions with following arguments and associated computation per subject for different time ranges (e.g. day, study period, ...).

For BGM data, at least 10 days data for each period are needed for each time period for the analysis. The time window for baseline is defined as the first 14 days of the study. The time window for 3 month is defined as the last 14 days of the third month. The time window for end of study is defined as the last 14 days of the sixth month. The start and end of time window may be manually adjusted based on the actual visit time.

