5.2.10 Approaches and Analyses for Missing Data and Other Data Issues

5.2.10.1 Glycaemic Data

Glycaemic data will only be included for analysis if 70% of the expected data is available, i.e. at least ten days over each 14 days period with at least one BGM measure.

Missing glycaemia data will be imputed using median value computed per period per subject when data is not available for a given day only if the data meet the availability of 70% of the expected data requirement.

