5.2.10.2 Insulin Data

Insulin data will only be included for analysis if 70% of the expected data is available, i.e. at least ten days over each 14 days period with at least one basal Insulin dose record and at least ten days over each 14 days period with at least one bolus Insulin dose record. In case a patient did not use boluses, only basal requirements will have to be fulfilled. The pattern of basal and bolus doses can be different (e.g. a day with basal information can have no bolus information).

Missing basal and bolus insulin data will be imputed separately, before TDD computation, using median value computed per period per subject when data is not available for a given day only if the data meet the availability of 70% of the expected data criteria.

6 Summary of General Study Data

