6.4 Device Failure, Malfunctions and Defects

A list of Device Failure will be provided.

7 Safety Analysis

A list of AE will be provided.

8 References

[1] R Core Team. *R: A Language and Environment for Statistical Computing*. R Foundation for Statistical Computing, Vienna, Austria, 2016. URL <https://www.R-project.org/>.

9 Appendix

Example tables are shown below. These tables are from previous studies and just for example only.

A Tables

Table A.0.1: Population Disposition

Subject Information	Number	Comments
Subjects Enrolled and Screened		
Subjects Randomized		
Subjects Who Completed the 45 day visit		
...		
Subjects Who Completed the Study		

Table A.0.2: Demographics (Randomized Subjects)

Characteristic		
Age	Mean	58.3
	Median	58.5
	SD	10.3
	Min, Max	34, 78
	Total Count	58
Gender		
	Female	31 (53.4%)
	Male	27 (46.6%)

Note: Demographics will also be provided stratified per site.

Table A.0.3: Summary Statistics for 24 Hour Average Blood Glucose (mg/dL)

Time	Characteristic		
Baseline	BG (Mean)		
Baseline	Mean	173.73	
Baseline	95% Mean CI	163.51, 184.71	
Baseline	Median	173.89	
Baseline	SD	40.47	
Baseline	Min, Max	85.13, 279.38	
Baseline	Total Count	57	
3 months	BG (Mean)		
3 months	Mean	173.73	
3 months	95% Mean CI	163.51, 184.71	
3 months	Median	173.89	
3 months	SD	40.47	
3 months	Min, Max	85.13, 279.38	
3 months	Total Count	57	
End of Study	BG (Mean)		
End of Study	Mean	178.64	
End of Study	95% Mean CI	166.46, 192.89	
End of Study	Median	167.83	
End of Study	SD	50.37	
End of Study	Min, Max	106.85, 397.94	
End of Study	Total Count	57	

Table A.0.4: Between-Time Point Comparisons for 24 Hour Average Blood Glucose Based on Linear Mixed Model.

Comparison	Estimate	Lwr	Upr	p.value	Result
3 months vs. Baseline	11.28	-3.11	25.67	0.122	No Sig. Diff.
End of study vs. Baseline	-2.16	-17.33	13.01	0.776	No Sig. Diff.

Table A.0.5: Summary Statistics for Number of Hypoglycemic Events

Period	Characteristic	
Baseline	Number of Hypoglycemic Events	
Baseline	0	53 (98.1%)
Baseline	1	1 (1.9%)
Baseline	Total	54
Baseline	Number of Severe Hypoglycemic Events	
Baseline	0	42 (77.8%)
Baseline	1	8 (14.8%)
Baseline	2	2 (3.7%)
Baseline	3	2 (3.7%)
Baseline	Total	54
Baseline	Incidence of Hypoglycemic Events	
Baseline	N	53 (98.1%)
Baseline	Y	1 (1.9%)
Baseline	Total	54
Baseline	Incidence of Severe Hypoglycemic Events	
Baseline	N	42 (77.8%)
Baseline	Y	12 (22.2%)
Baseline	Total	54
Baseline	Rate of Hypoglycemic Events	
Baseline	Mean	0.02
Baseline	Median	0.00

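### The daily glucose and diary-based TDD models have subject as their only random effect, so the end-of-study versus baseline CI is too narrow if subjects shift unequally, days are positively correlated within a period, or median-filled days count as data

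*SAP*

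**What the plan says.** SAP 5.2.4 (24-hour average glucose) states that "subject will be a random effect, time period (baseline, 3 months or end of study), day in each time period and lipohypertrophy" form the model, the last three as fixed effects. SAP 5.2.3 (TDD) is parallel: "subject will be a random effect, time period (baseline, 3 months or end of study), day in each time period, and lipohypertrophy". Both sections report the difference between baseline and end of study with a two-sided 95% CI. Interactions between the fixed effects are investigated and kept only if significant.

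On the data that feed these models:

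- SAP 5.1.3 defines three 14-day windows and requires at least 10 days of data in each. Glucose variables come from "associated computation per subject for different time ranges (e.g. day, study period", so a period-level value is already foreseen.
- SAP 5.1.1 takes TDD from the diary and from the CRF: "The data from the two sources will be analyzed separately". Under protocol 7.5 the diary is completed daily in the two-week windows, whereas the CRF holds one previous-day dose per visit.
- SAP 5.2.10.1: "Missing glycaemia data will be imputed using median value computed per period per subject when data is not available for a given day", provided the 10-of-14-day rule is met. SAP 5.2.10.2: "Missing basal and bolus insulin data will be imputed separately, before TDD computation, using median value computed per period per subject", under the same proviso.

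Neither the SAP (5.2.3, 5.2.4, 5.2.9, 5.2.10) nor protocol 10.2 mentions a subject-by-period random effect, a random slope, a residual correlation structure or a robust standard error. Neither says that these two models will be fitted to one value per period.

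**The concern.** The quantity of interest is a within-subject comparison of two periods. A random intercept for subject cancels out of that comparison. What remains is how differently subjects' levels move between periods, plus day-to-day noise averaged over the days. The model as written has no term for the first part, so that variation falls into the daily residual and is divided by about 14 as though it were fresh noise each day. The fixed day effect does not absorb it, because it is common to all subjects. A period-by-lipohypertrophy (LH) interaction, if kept, removes only the difference in mean shift between the two LH groups.

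Positive serial correlation between days acts in the same direction. So do filled days entered as rows: they add to the count of observations and shrink the residual without adding information.

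At stake are the CI and the p < 0.05 rule of SAP 5.2.9 for two secondary endpoints, 24-hour average glucose and diary-based TDD. A change could be called significant more often than the nominal error rate allows.

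**Working it through.** **The plan's own figure.** The only sample size in the documents is for HbA1c (SAP 2.3: decrease 0.4%, SD of paired differences 1.2%, 80% power, alpha 0.05). An exact two-sided one-sample t-test gives n = 73 with power 80.2%, so the figure reproduces. It does not involve the daily models.

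**Inputs.** n = 73 subjects (SAP 2.3), K = 3 periods and m = 14 days (SAP 5.1.3). Assumed, because the documents give no values: s² = day-to-day variance within subject and period; τ² = subject-by-period variance; r = τ²/s². The SD of a subject's true change between two periods, in units of the day SD, is √(2r).

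**Formulae (balanced data, random intercept, period and day fixed).**

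- Correct variance of the contrast: 2(τ² + s²/m)/n.
- Variance reported by the planned model: 2[s² + τ²(K−1)m/(Km−1)]/(mn), where (K−1)m/(Km−1) = 28/41 = 0.683.
- Hence (correct SE / planned SE)² = (14r + 1)/(1 + 0.683r).
- Type I error = 2[1 − Φ(1.96 / SE ratio)].

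Example at r = 0.0625: (0.875 + 1)/(1 + 0.0427) = 1.798; SE ratio 1.34; 1.96/1.34 = 1.46; type I error 14.4%.

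**Unequal shifts alone.**

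| r | √(2r) | SE ratio | Type I, formula | Type I, simulated (4,000 trials) | One mean per period, simulated |
|---|---|---|---|---|---|
| 0 | 0 | 1.00 | 5.0% | 5.0% | 4.9% |
| 0.0625 | 0.35 | 1.34 | 14.4% | 13.6% | 4.7% |
| 0.25 | 0.71 | 1.96 | 31.7% | 31.3% | 4.6% |
| 0.5625 | 1.06 | 2.53 | 43.9% | 44.5% | 4.7% |

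Solving the formula for fixed error rates gives 6% at r = 0.0065 (√(2r) = 0.11), 10% at r = 0.032 (0.25) and 20% at r = 0.108 (0.47). With 10 days instead of 14, the four rows become 5, 12, 26 and 37%.

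In one simulated data set at r = 0.25, the fitted SE of the contrast was 0.047 with a random intercept only. It was 0.086 with a subject-by-period effect added and 0.084 from paired differences of period means. The two mixed models gave the same point estimate.

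**Serial correlation alone (r = 0).** Let D = 1 + 2Σ(1 − k/14)ρᵏ, summed over k = 1 to 13. The squared SE ratio is 41D/(42 − D). At ρ = 0.2, D = 1.455, the SE ratio is 1.21 and type I error is 10.6%. At ρ = 0.1 and 0.4 it is 7.5% and 19.0%. At ρ = −0.3 the CI is too wide instead: simulated type I error was 0.8%.

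**Median filling alone (r = 0, independent days, 12,000 simulated trials each).**

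| Share of subject-periods with filled days | 1 day | 2 days | 4 days |
|---|---|---|---|
| All (upper bound) | 6.5% | 9.0% | 15.3% |
| Half | 5.7% | 6.7% | 9.7% |
| A quarter | 5.2% | 5.8% | 7.1% |

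Four days is the most that the 10-of-14-day rule permits. Analysing one mean of available days gave 4.8–5.0% throughout.

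**The case against.** **The size cannot be fixed from the documents.** This stands. Every r, ρ and missing-day rate above is an assumption. For glucose, one meter reading is enough for a day to count (SAP 5.2.10.1) and about four are recommended (protocol 7.5). A daily mean of so few readings is noisy, which pushes r down. The 32–44% rows are not expected values.

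**A reader might infer that any correlation between days narrows the CI.** It does not. Correlation that is constant across all of a subject's days is absorbed by the random intercept, and negative serial correlation widens the interval.

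**A reader might infer that the protocol documents unequal shifts for both endpoints.** It supports them for insulin dose only. Patients may change their dose individually (protocol 7.5, Visit 1). The physician may recommend a lower TDD depending on the patient's condition (7.6). Reductions of as much as 20% are described for patients who stop injecting into LH areas (7.7). Part of that last contrast lies between LH groups, and a period-by-LH interaction would take it up if it proves significant; variation within each LH group remains. For glucose, unequal shifts are plausible but not documented.

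**A richer model may have been intended.** A random intercept is the ordinary reading of the text, but the code is not shown. If more was meant, it should be written down. Residual plots (SAP 5.2.9) need not reveal the problem, and the remedy given there is transformation. The example tables do not settle it: SAP section 9 says "These tables are from previous studies and just for example only".

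**The consequences are limited.** This is so. SAP 2.6 says "There is no acceptance criteria for this study", and the primary endpoint is untouched.

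**Conclusion.** The concern holds in conditional form. As specified, the models for 24-hour average glucose and diary-based TDD give too narrow a CI for end of study versus baseline if any of three conditions applies: subjects shift by different amounts, days within a period are positively correlated beyond the subject effect, or median-filled days are entered as observed rows. With none of them present, the type I error is the nominal 5%.

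How much this matters depends on variances that the documents do not give. A spread of true changes of a quarter of the day-to-day SD is enough to double the error rate; below about a tenth the effect is negligible. Median filling is usually the smaller contributor. The documents do not support a claim that the reported intervals will be badly wrong, only that nothing in the specification protects them.

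HbA1c (one value per period, no day term), CRF-based TDD (one value per visit) and n = 73 are not affected. This should be fixed before analysis, but it does not threaten the primary conclusion.

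**What to change.** - **SAP 5.2.4 and 5.2.3 (diary data):** choose one of two options. Either specify random effects for subject and subject-by-period, with a residual correlation between days within a period, or analyse one mean of observed days per subject per period. The period-level glucose value is already provided for in 5.1.3. For diary TDD, use mean basal plus mean bolus for each subject and period.
- **SAP 5.2.10:** keep the 10-of-14-day rule, but do not enter median-filled days as observed rows.
- **SAP 5.2.3 (CRF data):** omit the day term, since there is one value per visit.

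The cost is SAP wording and a few lines of code, with no new data and no change in sample size. The downside is wider CIs for these two secondary endpoints wherever one of the three conditions holds. Where none does and the data are complete, the SE ratio is 1.0, so little precision is lost.

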5.2.5 Hypoglycemia

Summary statistics will be provided for the five categories of hypoglycemia events defined in Section 5.1.2. If data permits, the distribution of the hypoglycemia events during the night(12am to 6am) and during

the day (6am to 12am) will be summarized. The distribution by study month will be summarized too.

5.2.6 Injection Techniques

If data permit, a logistic mixed effect models will be used evaluate the effect of personalized teaching of the optimal insulin injection technique in conjunction with the use of disposable BD Micro-Fine Plus 32G pen needles on the percentage of subject correctly alternating injection sites. In the model, subject will be a random effect, time period (baseline, 3 months or end of study) and lipohypertrophy will be fixed effects. Two-way interactions between fixed effects will be investigated. Only significant interactions will be included in the model. Models will be used to compute estimated mean, difference between baseline and end of study, and corresponding two-sided 95% CI for responses of interest. Additional information recorded in the CRFs will be summarized.

Similar approaches will be used for percentage of subject using needles repeatedly and subject injecting into lipohypertrophy areas.

5.2.7 Change of lipohypertrophy

If data permit, a logistic mixed effect models will be used evaluate the effect of personalized teaching of the optimal insulin injection technique in conjunction with the use of disposable BD Micro-Fine Plus 32G pen needles on the percentage of subject with lipohypertrophy. In the model, subject will be a random effect, and time period (baseline, 3 months or end of study) will be fixed effects. Models will be used to compute estimated mean, difference between baseline and end of study, and corresponding two-sided 95% CI for responses of interest. Similar approaches will be used for lipohypertrophy size (length and width in mm) and localization (if applicable).

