7.1. Standards for the clinical trial

To allow for 73 evaluable subjects at 6 months follow up, a total of up to 90 patients will be enrolled (the statistical power of the study is provided in a section below, dedicated to statistical analysis). Each center will be offered to supply a sufficient number of patients as study subjects (up to 15 patients). Approximately half of these patients will be with lipohypertrophy (LH), and half will be without. Ideally, each center should recruit half of their patients with and half of their patients without LH. The Sponsor will monitor if the overall balance of 50%/50% is maintained

and will advise study centers accordingly. The main goal is to have an equal distribution across the study, not necessarily per site, however, each study center should have at least a distribution of 1/3 versus 2/3 in each group. The optimal injection technique and choice of needle length is based on the Russian Procedural Guidelines on injection techniques and infusions used in the treatment of diabetes mellitus [1]. These Guidelines, in turn, are based on recently published international guidelines by the Forum for Injection Technique Therapy Expert Recommendations (FITTER) [5].

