2.1 Study Design

A total of 90 patients will be enrolled. Each center will be offered to supply a sufficient number of patients as study subjects (up to 15 patients). Approximately half of these patients will be with lipohypertrophy (LH), and half will be without. Ideally, each center should recruit half of their patients with and half of their patients without LH. The Sponsor will monitor if the overall balance of 50%/50% is maintained and will advise study centers accordingly. The main goal is to have an equal distribution across the study, not necessarily per site, however, each study center should have at least a distribution of 1/3 versus 2/3 in each group. The optimal injection technique and choice of needle length is based on the Russian Procedural Guidelines on injection techniques and infusions used in the treatment of diabetes mellitus. These Guidelines, in turn, are based on recently published international guidelines by the Forum for Injection Technique Therapy Expert Recommendations (FITTER).

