2.2 Study Population

The selection of patients will not be influenced by race, religion, socio-economic and other factors. Approximately 50% of the subjects to be enrolled will have lipohypertrophy areas and 50% of the subjects will not.

Inclusion criteria:

- Type 1 or type 2 diabetes mellitus;
- Patients (male and female) of 18 years of age and over;
- At least 1 year of experience with insulin self-administration;
- Use of insulin pen for insulin injections;
- HbA1c > 7.5% measured at study entry or maximally 30 days prior to study entry;
- BMI below 40 kg/m² at study entry;
- Daily self-control of blood glucose level;
- Access to the internet for watching video lessons;
- Only outpatients are eligible for the study;
- Availability of the patient's signed informed consent for inclusion in the study.

Exclusion criteria:

- Pregnant women or women planning to become pregnant during the time of study, breastfeeding women;
- Subjects using an insulin pump;
- Those using treatment with a GLP-1 receptor agonists alone;
- Subjects not fluent in Russian (reading and writing);
- Patients at high risk for ketoacidosis and/or hyperglycemia;
- Psychic, physical or any other reasons hampering patient participation in the study (based on the reasonable opinion of the physician-investigator).

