3.1 Intended Statistical Software

This document was generated with R version 4.0.2 (2020-06-22) [1] and the following packages (version) were used: assertthat (0.2.1), backports (1.2.0), base (4.0.2), BD basics (0.3.3), broom (0.7.3), cellranger (1.1.0), cli (2.2.0), colorspace (2.0.0), compiler (4.0.2), crayon (1.3.4), datasets (4.0.2), DBI (1.1.0), dplyr (2.0.0), dplyr (1.0.2), ellipsis (0.3.1), fansi (0.4.1),forcats (0.5.0), fs (1.5.0), generics (0.1.0), ggplot2 (3.3.2), glue (1.4.2), graphics (4.0.2), grDevices (4.0.2), grid (4.0.2), gtable (0.3.0), haven (2.3.1), hms (0.5.3), httr (1.4.2), jsonlite (1.7.2), lifecycle (0.2.0), lubridate (1.7.9.2), magrittr (2.0.1), methods (4.0.2), modelr (0.1.8), munsell (0.5.0), pillar (1.4.7), pkgconfig (2.0.3), plyr (1.8.6), purrr (0.3.4), R6 (2.5.0), Rcpp (1.0.5), readr (1.4.0), readxl (1.3.1), reprex (0.3.0), rlang (0.4.9), rstudioapi (0.13), rvest (0.3.6), scales (1.1.1), stats (4.0.2), stringi (1.5.3), stringr (1.4.0), tibble (3.0.4), tidyverse (1.1.2), tidyselect (1.1.0), tidyverse (1.3.0), tools (4.0.2), vctrs (0.3.5), withr (2.3.0), xml2 (1.3.2), xtable (1.8.4).

The study analysis will be conducted within the same environment or more recent versions.

4 Analysis Population Set(s)

- Intent-to-treat (ITT) population: All subjects who have been enrolled in this study.
- Per-Protocol (PP) population: The ITT population without any major protocol deviations. A major protocol deviation is defined as a subject not meeting the inclusion/exclusion criteria.

The primary analysis population is the ITT population. Additional analyses on the PP population may be done post-hoc per team's request.

5 Statistical Analysis/Calculations

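### The planned lipohypertrophy analysis gives one net change in a sample recruited to about 50/50, so it cannot separate resolution from new cases and its size follows the recruited share.

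*SAP*

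**What the plan says.** SAP 5.2.7 takes LH status as a binary response and models the effect of training "on the percentage of subject with lipohypertrophy". The terms are given in full: "In the model, subject will be a random effect, and time period (baseline, 3 months or end of study) will be fixed effects". The output is also specified: "Models will be used to compute estimated mean, difference between baseline and end of study, and corresponding two-sided 95% CI for responses of interest". The model is fitted only where the data allow. Similar methods are to be used for LH size and localization, where applicable.

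Section 5.2.7 names no subset and no split by LH status at Visit 1. The default in SAP Section 4 therefore applies: "The primary analysis population is the ITT population", with that population defined as "All subjects who have been enrolled in this study".

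The LH share at baseline is set by recruitment. SAP 2.1 says: "Approximately half of these patients will be with lipohypertrophy (LH), and half will be without". SAP 2.2 repeats the target. Protocol 7.1 adds "The Sponsor will monitor if the overall balance of 50%/50% is maintained", has the sponsor advise centers accordingly, and limits each center to a split no more uneven than 1/3 to 2/3.

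SAP 2.5.3 lists change in LH among the exploratory endpoints. Protocol Table 2 schedules the LH examination at Visits 1, 3 and 5.

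**The concern.** LH status at Visit 1 is a recruitment stratum here, not an observed prevalence. A patient recruited with LH can only keep it or lose it. A patient recruited without can only stay free of it or acquire it. One pooled contrast over time subtracts one flow from the other and weights each by the recruited share.

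Two problems follow. The reader cannot tell clearance of existing LH from prevention of new LH, although these are different results for a training program. The same patient-level effect also gives a different answer at a different recruited share, so the figure cannot be read as a resolution rate or carried to a clinic population with another LH prevalence. Avoiding injection into LH areas is part of the trial hypothesis (Protocol Section 6), so readers will look for this result.

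**Working it through.** **Inputs.** From the documents: q, the share with LH at Visit 1, is about 1/2 overall and 1/3 to 2/3 within a center; enrollment is 90, with 73 evaluable. Assumed, because the documents give no value: r, the proportion of patients with LH at Visit 1 who have none at month 6; and i, the proportion without LH at Visit 1 who have it at month 6.

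**The plan's own figures.** The SAP states no rate, sample size or power for LH. Its 73 belongs to HbA1c. It reproduces (two-sided one-sample t-test, difference 0.4, SD 1.2, power 0.802) but does not bear on this point.

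**Formula.** Prevalence is q at Visit 1 and q(1-r) + (1-q)i at month 6. The change is (1-q)i - qr.

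**Dependence on q.** Change in percentage points:

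| Assumed r / i | q = 1/3 | q = 1/2 | q = 2/3 |
|---|---|---|---|
| 30% / 10% | 6.7 - 10.0 = -3.3 | 5.0 - 15.0 = -10.0 | 3.3 - 20.0 = -16.7 |
| 20% / 10% | 6.7 - 6.7 = 0.0 | 5.0 - 10.0 = -5.0 | 3.3 - 13.3 = -10.0 |
| 30% / 30% | 20.0 - 10.0 = +10.0 | 15.0 - 15.0 = 0.0 | 10.0 - 20.0 = -10.0 |
| 30% / 0% | -10.0 | -15.0 | -20.0 |

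The last row shows that with no new cases the netting disappears, but the result still scales with q.

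**Netting at q = 1/2.** A change of -10 points arises from r/i of 20%/0% (0 - 10), 30%/10% (5 - 15) or 40%/20% (10 - 20).

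**Does the random subject effect help?** A random-intercept logistic model with fixed time was fitted to the expected baseline and month 6 table. In each case fitted, its odds ratio equalled the ratio of discordant pairs, (1-q)i/(qr). For 30%/10% this is 0.67, 0.33 and 0.17 at q = 1/3, 1/2 and 2/3. Since (1-q)/q falls from 2 to 1/2 over that range, the odds ratio is divided by 4 with no change in patient-level effect.

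**Reading the odds ratio.** Take r = 35%, i = 8% and q = 1/2. Month 6 prevalence is 0.5 x 0.65 + 0.5 x 0.08 = 36.5%, so the marginal odds ratio is 0.365/0.635 = 0.57. Using baseline and month 6 only, the discordant-pair odds ratio is 0.08/0.35 = 0.23, and simulated fits gave about 0.18 to 0.25. With all three visits, the result depends on an assumed month 3 pattern. In simulated samples of 90 (25 to 40 per scenario, 61-point quadrature), the median was about 0.1, with a random-intercept SD of 6 to 7, when month 3 changes persist. It was about 0.19, with an SD near 4, when month 3 status (20% resolved, 5% new) and month 6 status are independent given Visit 1 status.

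**Split by Visit 1 status.** Under 30%/10%, the answer is 30% and 10% at every q. Approximate 95% half-widths, 1.96 x sqrt(p(1-p)/n), are 13 and 9 points with 45 per group, and 15 and 10 points with about 36 per group (73 evaluable).

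**The case against.** The endpoint is exploratory, the model is conditional on the data, and SAP 2.6 sets no acceptance criteria. Nothing primary or secondary depends on the result. This stands and limits the weight of the point.

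The SAP foresees some instability. SAP 5.2.9 allows the random subject effect to be dropped if a discrete model does not converge, and provides for a difference in proportions where no stable model is available. Section 5.2.7 also asks for estimated means and differences, not only an odds ratio. This softens the concern about reading the odds ratio, although a model that converges with a very large variance might not trigger the fallback. Neither fallback removes the netting, because both still average over all subjects. McNemar's test (Protocol 10.2) uses the same discordant pairs. The per-LH-subgroup analysis in Protocol 10.2 is attached to HbA1c and insulin dose and requires a significant subgroup effect.

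A reader might infer that the pooled contrast is invalid and should be removed. It is not invalid: it is a correct within-sample net change. A reader might also infer that a real benefit would be hidden. That would need substantial new LH among trained patients, and the documents support no such rate; with 35% resolved and 8% new, the pooled figure still falls from 50% to 36.5%. Finally, a subject-specific odds ratio further from 1 than the marginal one is normal for a random-intercept logistic model and is not in itself an error.

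The split has a weakness of its own. Patients selected as having LH can only lose it and the others can only gain it, so in a single-arm study examination error alone produces some apparent resolution and some apparent new LH.

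**Conclusion.** The point holds as a limit on interpretation that is cheap to repair. As written, SAP 5.2.7 yields a net change that cannot separate resolution from new LH and that scales with the recruited share: -3.3 to -16.7 points over q = 1/3 to 2/3 for the same assumed 30%/10%. The overall target is 1/2. The outer values are the limits for a single center and show the dependence; they are not a forecast of the final sample.

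The mechanism is arithmetic and needs no assumption beyond the analysis set. Section 5.2.7 does not itself say that all patients are included; this is read from the SAP's default population. Every size given here rests on assumed rates. In particular, a reader might take an odds ratio near 0.1 as what the planned model will give. It belongs to one assumed month 3 pattern; under the patterns tried, the range is about 0.1 to 0.25 against a marginal 0.57. The primary HbA1c conclusion is not affected.

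**What to change.** In SAP 5.2.7:

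- Make the main LH analysis the proportion resolved at months 3 and 6 among patients with LH at Visit 1, and the proportion with new LH at months 3 and 6 among patients without, each with an exact 95% CI.
- Show the table of Visit 1 status by month 6 status.
- State explicitly that LH size is analyzed in patients with LH at Visit 1. The present qualifier, where applicable, probably intends this but does not say so.
- Keep the pooled percentage only as a descriptive net change, labeled as belonging to the quota sample.
- Record as a limitation that detection error alone can produce apparent resolution and apparent new LH, because patients are selected on Visit 1 status and there is no control arm.

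Adding Visit 1 LH as a fixed effect to the existing model would not serve, because it determines the baseline response completely.

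The cost is a change of SAP wording and a few simple tables. The examinations at Visits 1, 3 and 5 already supply the data.
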